13.2.3 Serious Adverse Events (SAEs)

The number and percentage of participants, and total number of events, with SAEs including intussusception reported through 4 weeks after the last vaccination will be tabulated after any dose and after each dose for each vaccine group and overall by system organ class, preferred term, and severity (Table 43-45) and by system organ class, preferred term, and relationship to study vaccine (Table 46-48). Results will be tabulated for the safety population. For the percentage, and exact two-sided 95% CI will be provided using Clopper-Pearson method.

The number and percentage of participants experiencing SAEs including intussusception reported through 4 weeks after the last vaccination will be summarized after any dose and after each dose by MedDRA system organ class and preferred term (Table 49-51). This summary will be repeated for related SAE, and unsolicited AEs leading to hospitalization and deaths (Tables 52-56). Results will be tabulated for the safety population for each vaccine group and overall.

All SAEs will be listed (Listing 17).

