5.1.3 Continued Eligibility Confirmation for subsequent vaccination

The following events constitute absolute contraindications to rotavirus vaccination and all participants should be evaluated for these before administration of second dose of the study vaccine. If any of these events occur during the study, the participant must not receive additional doses of the vaccine but should be appropriately followed up for safety by the Investigator.

- Hypersensitivity reaction following the administration of the study vaccine.
- Any uncorrected congenital malformation of the gastrointestinal tract (such as Meckel's diverticulum) which is diagnosed after the first vaccination and that would predispose for intussusception.
- Infants with any history of intussusception.
- Severe combined immunodeficiency (SCID).
- Detection of one or more of the exclusion criteria during dosing period.

The following events constitute contraindications to administration of the study vaccine at that point in time; if any of these events occur at the time scheduled for vaccination, the participant may be vaccinated at a later date or withdrawn at the discretion of the Investigator.

- Acute disease and / or fever at the time of vaccination.
 - Acute disease is defined as the presence of a moderate or severe illness with or without fever. All vaccines can be administered to persons with a minor illness such as mild upper respiratory infection without fever.
 - Fever is defined as temperature $\geq 37.5^{\circ}$ C (99.5°F) on axillary setting.
- Gastroenteritis within 72 hours preceding the study vaccine administration.

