- 4. The parent/LAR will be instructed that if the participant later experiences an AE requiring medical care, the parent/LAR should inform the investigator as soon as possible and seek medical care as appropriate. If the participant visits a health care provider, the parent/LAR should be sure to inform the health care provider of participation in this study and give the health care provider the contact information for the investigator.
- 5. The data in the PIDC collected by the parents will be reviewed by the study physician/designee and entered in the CRF. Any solicited reaction extending beyond 7 days after vaccination will also be recorded on the PIDC/CRF with date of resolution (if available) and the highest severity during the occurrence. Also, unsolicited AEs will be captured up to 28 days after each vaccination and SAEs including suspicion of intussusception will be recorded at all times between first vaccination and last visits. These will be managed medically as needed.

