7.3 Final Study Visit (Day 85; +14)

The date for this visit will be calculated 28 days from the date of last vaccination. A maximum window period of +14 days will be allowed for this visit. Parents will be contacted for the participants who miss the scheduled visit date. The following procedures will be conducted:

- 1. Study staff will confirm participant's identity.
- 2. Review / update address and contact details.
- 3. Check for any adverse events since last visit and record them in the source note and eCRF if applicable. Update medical history including follow-up of prior SAEs. Ensure all ongoing AEs are followed up as per the protocol.
- 4. Collection and review of the diary cards if not already collected by field worker earlier.
- 5. Check for use/administration of any medication/vaccine since last visit. Any medication taken for the treatment of the illness or vaccine administered will also be recorded in the relevant section of the CRF.
- 6. Perform physical examination.
- 7. Collect up to 2 mL of blood for immunological assay.
- 8. Review vaccination history and advise the parent/LAR on future vaccination of the infant.
- 9. Complete the study termination/completion form

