9.5 Guidelines for AEs

To improve the quality and precision of acquired AE data, the PI should observe the following guidelines:

- All AEs and SAEs will be recorded in the source document and eCRF for all participants throughout the study participation.
- A solicited symptom reported during the solicitation period as an SAE should be recorded on the PIDC and SAE forms.
- Whenever possible, use recognized medical terms when recording AEs on the AE CRF. Do not use colloquialisms and/or abbreviations.
- If known, record the diagnosis (i.e., disease or syndrome) rather than component signs, symptoms and laboratory values (e.g., record congestive heart failure rather than dyspnea, rales, and cyanosis). However, signs and symptoms that are considered unrelated to an encountered syndrome or disease should be recorded as individual AEs (e.g., if congestive heart failure and severe headache are observed at the same time, each event should be recorded as an individual AE).
- AEs occurring secondary to other events (e.g., sequelae) should be identified by the primary cause. A "primary" AE, if clearly identifiable, generally represents the most accurate clinical term to record. If a primary serious AE (SAE) is recorded, events occurring secondary to the primary event should be described in the narrative description of the case.

Acute Gastroenteritis→ Diarrhea→ Nappy Rash

The primary AE here is acute gastroenteritis.

- Death is an outcome of an event. The event that resulted in the death should be recorded and reported on the SAE CRF.
- For hospitalizations for surgical or diagnostic procedures, the illness leading to the surgical or diagnostic procedure should be recorded as the SAE, not the procedure itself. The procedure should be captured in the case narrative as part of the action taken in response to the illness.

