All SAEs reported from the time of first vaccination upto 4 weeks after last vaccination will be reported in the study. All SAEs must be reviewed and evaluated by a study clinician (SAE relationship to study vaccine must be evaluated as outlined in Section 9.4) and recorded on an SAE form and reported, as specified in Section 9.1010. All such SAEs should also be followed until satisfactory resolution or until the investigator deems the event to be chronic or the patient to be stable.

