9.10 Reporting Procedures

Serious Adverse Events

All SAEs must be documented and reported to POLYVAC or its designate, even if the investigator considers that the SAE is not related to treatment. The study clinician will complete a **Serious Adverse Event Form** within the following timelines of such events:

- All SAEs, whether related or unrelated, will be recorded on the Serious Adverse Event Form and notified to local IRB and sponsor by fax or email within 24 hours of site awareness.
- All deaths and immediately life-threatening events, whether related or unrelated, will be recorded on the Serious Adverse Event Form and reported to the MOH by fax or email within 7 days of site awareness.

• SAEs other than death and immediately life-threatening events (i.e., events resulting in hospitalization or prolongation of hospitalization, persistent or significant disability or incapacity, or other significant events determined by the investigator to be SAEs), regardless of relationship, will be reported reported to the MOH via fax or email by the site within 15 days of becoming aware of the event.

POLYVAC will be primarily responsible for medical monitoring of serious adverse events documented by the investigator. Medical Officers from PATH serving as technical consultants will review all serious adverse events and provide guidance regarding SAE management, including classification and reporting. Details for review and reporting of serious adverse events and other unanticipated problems will be in an SOP drafted prior to study initiation.

Reporting of AEs

Collected SAEs will be reported to responsible ethical review committees according to their requested timelines. An SOP for reporting to the responsible committees will be developed with reporting requirements and timelines prior to study initiation. It will be the investigator's responsibility to assure that all reportable events are reported to the proper authority, or to POLYVAC, and/or its designate in a timely manner and according to existing SOP. PATH technical consultants may assist the investigator with regulatory reporting, per the finalized SOP.

Other Unexpected Issues/Unanticipated Problems

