3.2.2 Secondary Endpoints

Immunogenicity

- Percentage of participants with seroconversion in serum anti-rotavirus IgA antibody concentrations 28 days after the second vaccination defined as follows:
 - For participants with a negative pre-vaccination IgA concentration (< 20 IU/ml), a positive post-vaccination IgA concentration (≥ 20 IU/ml);
 - For participants with a positive pre-vaccination IgA concentration, a post-vaccination IgA concentration at least 4 times as high as the pre-vaccination IgA concentration.
- Percentage of participants with seropositivity at baseline and 28 days after the second vaccination. Seropositivity is defined as serum IgA antibody concentration ≥ 20 IU/ml.

Safety

- Immediate adverse events, within 30 minutes after each vaccination.
- Unsolicited AEs from vaccination through four weeks after each dose.
- Serious adverse events (SAEs) and intussusception from first vaccination through four weeks after the last vaccination.

4. Investigational Plan

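### Read literally, the SAE and intussusception window closes on Day 29 for an infant who receives only Dose 1, so an SAE after that day which causes Dose 2 to be withheld is left out of the SAE summaries

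*SAP*

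**What the plan says.** **Sections that set the limit.** SAP 3.2.2 defines the endpoint as "Serious adverse events (SAEs) and intussusception from first vaccination through four weeks after the last vaccination", and Protocol 3.2.2 matches it. SAP 13.2.3 carries the limit into the tables: participants and events "with SAEs including intussusception reported through 4 weeks after the last vaccination will be tabulated after any dose and after each dose". Protocol 9.2 and 12.4.3 use the same period. Protocol 9.9 words it as a reporting rule: "All SAEs reported from the time of first vaccination upto 4 weeks after last vaccination will be reported in the study". None of these sections says what the last vaccination is for an infant who gets one dose.

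**Sections that are wider.** Protocol 7.1 says that "SAEs including suspicion of intussusception will be recorded at all times between first vaccination and last visits", and 7.2 repeats this. Protocol 9.5 says "All AEs and SAEs will be recorded in the source document and eCRF for all participants throughout the study participation". Protocol 9.10 sets no dose-based cut-off: "All SAEs must be documented and reported to POLYVAC or its designate".

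**Sections that create one-dose infants.** Protocol 5.1.3 lists events, intussusception among them, after which "the participant must not receive additional doses of the vaccine but should be appropriately followed up for safety by the Investigator".

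**Final visit.** Protocol 7.3 is headed Day 85 (+14), but its text reads "The date for this visit will be calculated 28 days from the date of last vaccination".

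**The concern.** In a fully dosed infant the window is continuous and nothing falls between the doses. When Dose 2 is not given, Dose 1 becomes the last vaccination and the window closes before the Dose 2 visit is due. An event in the following weeks is then counted or not according to its consequence: in if the infant goes on to Dose 2, out if the event stopped dosing.

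For a live oral rotavirus vaccine, an SAE that stops dosing is one that a reader of the SAE tables most needs to see. The infant remains in the safety population, which requires only one dose (SAP 7.1). The numerator would therefore lose the event while the denominator keeps the infant, in the percentage and in its Clopper-Pearson interval.

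**Working it through.** **Inputs.** Dose 1 is Day 1 (Protocol 7.1). Dose 2 is due 56 days later, with a window of +14 days (Protocol 7.2). The final visit is 28 days after the last vaccination, +14 (Protocol 7.3). The SAE window ends 28 days after the last vaccination.

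**Reproducing the schedule.** Dose 2: 1 + 56 = Day 57. Final visit: 57 + 28 = Day 85. Both match the schedule of events. The latest in-window Dose 2 is 57 + 14 = Day 71.

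**Window by number of doses, literal reading.**
- Two doses: Day 1 to 57 + 28 = Day 85, or to 71 + 28 = Day 99 if Dose 2 is on Day 71.
- One dose: Day 1 to 1 + 28 = Day 29.

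**Uncovered days before the Dose 2 visit.**
- Visit on Day 57: Day 30 to Day 56, which is 56 − 29 = 27 days, or 27/56 = 48% of the days before the visit.
- Visit on Day 71: Day 30 to Day 70, which is 70 − 29 = 41 days, or 41/70 = 59%.

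**Example.** An infant has intussusception on Day 40. Protocol 5.1.3 bars further doses, so the window closed on Day 29 and the event is outside it. An infant with a different SAE on Day 40, not listed in 5.1.3, who receives Dose 2 on Day 57 has a window to Day 85, and the event is counted.

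**Do other tables recover the event?** SAP 13.2.2 limits the unsolicited AE tables to four weeks after each vaccination, so Day 40 is outside them too. Table 42 (AEs that stop vaccination while follow-up continues) is introduced there as a repeat of that summary, so it cannot be relied on to show the event. Listing 17 covers all SAEs without a window, and SAP 13.2.4 tabulates all deaths without one.

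**Final visit.** For an infant with Dose 1 only, the text of Protocol 7.3 gives 1 + 28 = Day 29, and 29 + 14 = Day 43 at the latest. Both precede the Day 57 visit at which Dose 2 would be refused, and both disagree with the section's own Day 85 heading.

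**Scale.** The earlier ROTAVIN-M1 phase III trial reported 3 SAEs in 800 infants (Protocol 2.5.3), which scales to 3/800 × 825 = 3.1 here. At the 1-7 attributable intussusceptions per 100,000 cited in Protocol 2.7.1, 550 liquid-formulation recipients would have 0.006 to 0.039 cases. How many SAEs would fall in the gap and also stop Dose 2 is not given and cannot be derived. Each one omitted would lower the liquid-group percentage by 1/550 = 0.18 percentage points.

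**The case against.** **The anchor could mean the scheduled second dose.** No section says the last dose received. The primary objective speaks of the last dose of a two-dose schedule, and Protocol 8.2 uses last vaccination to date the post-Dose-2 blood sample. This is a fair reading, so the exclusion follows from the literal wording and is not an explicit rule for one-dose infants. But Protocol 7.3 counts from the date of the last vaccination, and a dose never given has no date. A programmer needs the term defined either way.

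**Most SAEs do not bar Dose 2.** This stands. Protocol 5.1.3 lists specific events. Acute illness allows later vaccination or withdrawal at the investigator's discretion, and 7.4 allows Dose 2 outside its window. An SAE followed by Dose 2 is inside the window on any reading.

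**The event is visible elsewhere.** This also stands. It is recorded, reported to the sponsor, sent to expedited review if it is intussusception or a related SAE (Protocol 9.12), and listed. Protocol 12.4.3 also promises a detailed description of SAEs and of discontinuations due to AEs. The titles of Tables 43-54 and of Table 57 carry no four-week limit. However, the SAP text that specifies Tables 43-54 does carry the SAE limit, so the titles do not settle the matter.

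**Stronger readings that the documents do not support.**
- A reader might apply the 10% dropout rate of Protocol 12.2 to the missing 56 days (Day 29 to Day 85) and obtain 55 × 56 / (550 × 84) = 6.7% of person-time lost. Dropouts who leave the study contribute no later time under any window, and the SAP reports percentages of participants, not person-time.
- A reader might infer bias between the arms. That needs arms that differ in how often Dose 2 is withheld for such events, and nothing in the documents indicates this.
- A reader might cite the three SAEs of the earlier trial, all more than 40 days after vaccination. The protocol does not say which dose they followed or that any stopped Dose 2. They show only that SAEs occur beyond 28 days.
- A reader might conclude that a one-dose infant can have no final visit. Protocol 8.1 calls for clinician evaluation on Day 85, and 7.4 encourages the remaining safety follow-up when further doses are declined.

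**Conclusion.** The point holds as a defect in the endpoint wording, in the windowed SAE summaries (Tables 43-54) and in the reporting sentence of Protocol 9.9. It rests on reading last vaccination as the last dose actually given. On that reading, 27 to 41 days before the Dose 2 visit are uncovered for a one-dose infant, and inclusion of an SAE depends on whether it stopped dosing. On the other reading the anchor is still undefined for that infant. In both cases the limit conflicts with Protocol 7.1, 7.2 and 9.5.

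The practical effect is small: few events are expected, their number is unknown, and they remain in the database, in safety oversight and in Listing 17. It is still worth correcting before the tables are programmed, because the affected events would be among the most informative in the safety summary.

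**What to change.** 1. In SAP 3.2.2 and 13.2.3, define the SAE and intussusception tabulation window as first vaccination through the last study contact for every vaccinated participant, whether or not Dose 2 was given. Tabulate all such SAEs in Tables 43-54.
2. State in the SAP that an SAE occurring before any Dose 2 is assigned to the after-Dose-1 tables.
3. Align Protocol 3.2.2, 9.2, 9.9 and 12.4.3 with the recording rules in 7.1, 7.2 and 9.5.
4. Separately, reconcile the text of Protocol 7.3 with its Day 85 heading and with 5.1.3 and 7.4 for infants who do not receive Dose 2. The trial team must decide what that schedule is.

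The cost is wording in both documents and one programming rule. The SAEs are already collected, so items 1 to 3 need no new procedure. Sample size, power and type I error do not change.

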13.2.4 Deaths

All deaths will be tabulated by system organ class and preferred term (Table 56) and listed (Listing 18).

13. Other Safety Analyses

An overall safety summary of AEs (Table 57) will be included. This table will be based on the safety population for each vaccine group and overall.

14.1 Vaccination

The study vaccine (ROTAVIN or ROTAVIN-M1) is administered twice during the study on Day 1 and Day 57. Vaccination information will be summarized by vaccine group and overall (Table 58) and will be listed (Listing 19). Participants randomized but not vaccinated are summarized in Table 1.

14.2 Solicited Reactions

In addition to the primary analyses, solicited adverse events will be tabulated by onset day and duration in days after any dose and after each dose by vaccine group and overall (Table 59-61). These analyses are based on total number of events. Results will be tabulated for the safety population for participants with available data.

The number and percentage of participants experiencing an ongoing event at Day 7 will be tabulated after any dose and after each dose by vaccine group and overall (Table 62-64). These analyses will be tabulated for the safety population for participants with available data.

14.3 Vital Signs

Vital signs including heart rate, axillary temperature, and respiratory rate, are assessed at all visits. Further, vital signs are assessed 30 minutes after each vaccination.

For each visit, vital sign parameters will be summarized using mean, standard deviation (SD), median, and range (minimum, maximum). Change from baseline will also be presented. The number and percentage of participants with normal, abnormal and not clinically significant and abnormal and clinically significant vital signs will also be included (Tables 65-67). Results will be tabulated by vaccine group and overall for the safety population for participants with data at the given visit.

The number and percentage of participants with normal assessment pre-dose and abnormal CS/NCS assessment 30 Min post-dose will be summarized will be tabulated by vaccine group and overall for the safety population for participants with available data Table 68-70.

Boxplots will be used to show vital sign measurements over time graphically (Figure 11 through Figure 13).

Vital sign measurements and assessments made at each visit and 30 minutes post each vaccination will also be listed. (Listing 20).

14.4 Physical Examination

General appearance, head & neck, eyes, ears, nose & throat, lymph nodes, skin and subcutaneous tissue, respiratory, cardiovascular, gastrointestinal, genitourinary, central nervous system, and musculoskeletal and connective tissue, and other systems are assessed as part of physical examination at all visits. Further, targeted physical examination may be assessed 30 minutes after each vaccination, if indicated.

For each visit, the number and percentage of participants with normal, abnormal and not clinically significant, and abnormal and clinically significant body systems will be summarized (Table 71).

Summaries will be presented for each vaccine group and overall. Results will be tabulated for the safety population for participants with data at the given visit.

Physical examinations made at each visit and post each vaccination will also be listed (Listing 21).

14. References

1. Berger, R.L. and Hsu, J.C. 1996, "Bioequivalence trials, intersection-union tests, and equivalence confidence sets." *Statistical Science*, 11, 283-319.

15. Tables, Listings and Figures

16.1 Tables

Table 1: Participant Disposition

	ROTAVIN	ROTAVIN-M1	Total
Screened ^a			x
Screen Failure ^a			x
Enrolled ^a			x
Randomized	x (x)	x (x)	x (x)
Randomized but not Vaccinated	x (x)	x (x)	x (x)
Received Dose 1	x (x)	x (x)	x (x)
Received Dose 2	x (x)	x (x)	x (x)
Received all Doses	x (x)	x (x)	x (x)
Safety Population	x (x)	x (x)	x (x)
Full Analysis (FA) Population	x (x)	x (x)	x (x)
Per Protocol (PP) Population	x (x)	x (x)	x (x)
Number of Participants who Completed			
Visit 1	x (x)	x (x)	x (x)
Visit 2	x (x)	x (x)	x (x)
Visit 3	x (x)	x (x)	x (x)
Completed Study	x (x)	x (x)	x (x)
Early Terminated from Study	x (x)	x (x)	x (x)
Parent withdrew consent	x (x)	x (x)	x (x)
Investigator discretion	x (x)	x (x)	x (x)
...	x (x)	x (x)	x (x)
...	x (x)	x (x)	x (x)
Discontinued the Vaccine	x (x)	x (x)	x (x)
Parent withdrew consent	x (x)	x (x)	x (x)
Investigator discretion	x (x)	x (x)	x (x)
...	x (x)	x (x)	x (x)

	ROTAVIN	ROTAVIN-M1	Total
x (%) is presented, unless otherwise specified.			
^a Number of participants is presented.			
Percentages are based on the total number of randomized participants in the enrolled population in each vaccine group and overall.			

Table 2: Screen Failures

	Total N=xx	
	X	%
Number of Screen Failures	X	X.X
Number Who Did Not Meet Eligibility Criteria	X	X.X
Inclusion Criteria Not Met	X	X.X
Healthy infants as established by medical history and clinical examination before entering the study.	X	X.X
Age: 60-91 days (both days inclusive) at the time of enrollment.	X	X.X
Parental/LAR ability and willingness to provide written informed consent.	X	X.X
Parent/LAR who intends to remain in the area with the child during the study period.	X	X.X
Exclusion Criteria Met	X	X.X
Presence of diarrhea or vomiting in the previous 72 hours or on the day of enrollment (temporary exclusion).	X	X.X
Presence of fever on the day of enrollment (temporary exclusion)	X	X.X
Acute disease at the time of enrollment (temporary exclusion)	X	X.X
Concurrent participation in another clinical trial at any point throughout the entire timeframe for this study.	X	X.X
Presence of significant malnutrition (weight-for-height z-score < -3SD median)	X	X.X
Presence of any systemic disorder (cardiovascular, pulmonary, hepatic, renal, gastrointestinal, hematological, endocrine, immunological, dermatological, neurological, cancer, or autoimmune disease) as determined by medical history and / or physical examination which would compromise the participant's health or is likely to result in nonconformance to the protocol.	X	X.X
History of congenital abdominal disorders, intussusception, or abdominal surgery.	X	X.X
Known or suspected impairment of immunological function based on medical history and physical examination.	X	X.X
Household contact with an immunosuppressed individual or pregnant woman.	X	X.X
Prior receipt of rotavirus or an intent to receive this vaccine from outside of the study center during study participation.	X	X.X
Prior receipt of EPI vaccination during past 7 days or plan to receive them within next 7 days.	X	X.X

A known sensitivity or allergy to any components of the study vaccine.	x	x.x
History of allergy to antibiotic kanamycin.	x	x.x
Clinically detectable significant congenital or genetic defect.	x	x.x
History of persistent diarrhea (defined as diarrhea that lasts 14 days or longer).	x	x.x
Receipt of immunoglobulin therapy and / or blood products since birth or planned administration during the study period.	x	x.x
History of chronic administration (defined as more than 14 days) of immunosuppressants including corticosteroids. Infants on inhaled or topical steroids may be permitted to participate in the study.	x	x.x
Any medical condition in the parent/LAR or infant which, in the judgment of the Investigator, would interfere with or serves as a contraindication to protocol adherence.	x	x.x
Other	x	x.x

N=Total number of participants who screen failed

x=Number of participants who screened failed

A participant who is a screen failure may not have satisfied multiple eligibility criteria; therefore, the sum of participants in the individual inclusion/exclusion criteria rows may not add up to the total number of participants who did not meet eligibility criteria.

Table 3a: Demographic and Baseline Characteristics – Safety Population

	ROTAVIN N=XX	ROTAVIN- M1 N=XX	Total N=XX	p-value ^a
Age (Days)				
n	x	x	x	0.xxxx
Mean (SD)	x.x (x.xx)	x.x (x.xx)	x.x (x.xx)	
Median	x	x	x	
Range (Min, Max)	x, x	x, x	x, x	
Ethnicity, N (%)				
Vietnamese	x (x)	x (x)	x (x)	0.xxxx
Chinese	x (x)	x (x)	x (x)	
Other	x (x)	x (x)	x (x)	
Gender, N (%)				
Male	x (x)	x (x)	x (x)	0.xxxx
Female	x (x)	x (x)	x (x)	
Birth Weight (kg)				
n	x	x	x	0.xxxx
Mean (SD)	x.xx (x.xxx)	x.xx (x.xxx)	x.xx (x.xxx)	
Median	x.x	x.x	x.x	
Range (Min, Max)	x.x, x.x	x.x, x.x	x.x, x.x	

N=Total number of participants in the FA population in each vaccine group and overall.
n=Number of participants with non-missing values
Percentages are based on the total number of participants in the FA population in each vaccine group and overall.
^a p-value based on the t-test or Fisher's exact test comparing ROTAVIN and ROTAVIN-M1®

Programming note: If there are missing values for any of the categorial parameters, then a separate row corresponding to "Missing" must be added under than category.

Table 3b: Demographic and Baseline Characteristics – FA Population

{This table will be similar to Table 3a}

Table 3c: Demographic and Baseline Characteristics – PP Population

{This table will be similar to Table 3a}

Programming note: If more than 10% of the FA population is excluded from the PP population, the description and comparability of the vaccine groups at baseline will be repeated on the PP population.

Table 4: Medical history by System Organ Class and Preferred Term – Safety Population

MedDRA System Organ Class Preferred Term	ROTAVIN N=XX x (%)	ROTAVIN-M1 N=XX x (%)	Total N=XX x (%)
Participants with at least one Medical History Event	x (x)	x (x)	x (x)
SOC1	x (x)	x (x)	x (x)
PT1	x (x)	x (x)	x (x)
PT2	x (x)	x (x)	x (x)
...	x (x)	x (x)	x (x)
SOC2	x (x)	x (x)	x (x)
PT1	x (x)	x (x)	x (x)
PT2	x (x)	x (x)	x (x)
...	x (x)	x (x)	x (x)

N=Total number of participants in the safety population

x=Number of participants with a medical history event

Percentages are based on the total number of participants in the safety population.

A participant may be counted in multiple rows within each system organ class; however, they will be counted only once in the overall row for the system organ class. Therefore, the sum of participants within each system organ class may not add up to the overall row for the system organ class.

All medical history terms coded and reviewed on MedDRA version XX.X.

Table 5: Other Medical History – Safety Population

	ROTAVIN N=XX x (%)	ROTAVIN-M1 N=XX x (%)	Total N=XX x (%)
Drug/vaccine allergy	x (x)	x (x)	x (x)
Yes	x (x)	x (x)	x (x)
No	x (x)	x (x)	x (x)
Participation in interventional drug research study or other vaccine clinical trial	x (x)	x (x)	x (x)
Yes	x (x)	x (x)	x (x)
No	x (x)	x (x)	x (x)
History on immunodeficiency in any house hold member	x (x)	x (x)	x (x)
Yes	x (x)	x (x)	x (x)
No	x (x)	x (x)	x (x)
Pregnancy in any family member living in the same household	x (x)	x (x)	x (x)
Yes	x (x)	x (x)	x (x)
No	x (x)	x (x)	x (x)

N=Total number of participants in the safety population
x=Number of participants with an event
Percentages are based on the total number of participants in the safety population.

Table 6: Protocol Deviations by Category – Safety Population

Protocol Deviation Category	ROTAVIN N=XX x (%), E	ROTAVIN-M1 N=XX x (%), E	Total N=XX x (%), E
Total	x (%), E	x (%), E	x (%), E
Incomplete vaccination: Subject declined further vaccination but safety follow up continued	x (%), E	x (%), E	x (%), E
Incorrect Informed consent process	x (%), E	x (%), E	x (%), E
Incorrect Procedure	x (%), E	x (%), E	x (%), E
Missed Procedures	x (%), E	x (%), E	x (%), E
Subject confidentiality compromised: Personal data of subject transmitted to unintended recipient/s	x (%), E	x (%), E	x (%), E
Temperature excursion	x (%), E	x (%), E	x (%), E
Visit Window Deviation: Post vaccination assessment done before protocol specified timeline	x (%), E	x (%), E	x (%), E
Other	x (%), E	x (%), E	x (%), E

N=Total number of participants in the safety population E=Total number of protocol deviations x=Number of participants with a protocol deviation Percentages are based on the total number of participants in the safety population.
			

If multiple protocol deviations are reported for a participant, the participant may be counted in multiple rows corresponding to the different protocol deviation categories; however, they will be counted only once in the "Total" row. Therefore, the sum of participants may not add up to the "Total" row.

Programming Note: Print only the categories that have data

Table 7: Protocol Violations by Category – Safety Population

Protocol Violations Category	ROTAVIN N=XX x (%), E	ROTAVIN-M1 N=XX x (%), E	Total N=XX x (%), E
Total	x (%), E	x (%), E	x (%), E
Did not meet I / E criteria but enrolled	x (%), E	x (%), E	x (%), E
Dosed when withdrawal / discontinuation criteria were met	x (%), E	x (%), E	x (%), E
Incomplete vaccination: Replacement dose not administered in case of vomiting within 5 mins of administration	x (%), E	x (%), E	x (%), E
Informed Consent Not Taken	x (%), E	x (%), E	x (%), E
Incorrect Informed consent process: LAR not used when required	x (%), E	x (%), E	x (%), E
Damaged / Expired IP / Quarantined kit used without prior approval	x (%), E	x (%), E	x (%), E
Missed Procedures	x (%), E	x (%), E	x (%), E
Randomized to wrong treatment arm: Dosed with wrong treatment arm at visit 1	x (%), E	x (%), E	x (%), E
Wrong treatment arm administered at second dose	x (%), E	x (%), E	x (%), E
Receipt of Prohibited Medications / vaccinations / Therapies	x (%), E	x (%), E	x (%), E
Safety reporting beyond regulatory timelines	x (%), E	x (%), E	x (%), E

Visit Window Deviation	x (%), E	x (%), E	x (%), E
Other	x (%), E	x (%), E	x (%), E

N=Total number of participants in the safety population
E=Total number of protocol violations
x=Number of participants with a protocol violation
Percentages are based on the total number of participants in the safety population as defined in the protocol.
If multiple protocol violations are reported for a participant, the participant may be counted in multiple rows corresponding to the different protocol violations categories; however, they will be counted only once in the "Total" row. Therefore, the sum of participants may not add up to the "Total" row.

Programming Note: Print only the categories that have data

Table 8: Analysis Populations

Analysis Population	Reason Participants Excluded	ROTAVIN	ROTAVIN-M1	Total
Safety Population	Number of participants	x (100.0%)	x (100.0%)	x (100.0%)
	Any Reason for Exclusion	x (xx.xx%)	x (xx.xx%)	x (xx.xx%)
	[Reason 1]	x (xx.xx%)	x (xx.xx%)	x (xx.xx%)
	[Reason 2]	x (xx.xx%)	x (xx.xx%)	x (xx.xx%)
	...			
Full Analysis Population	Number of participants	x (100.0%)	x (100.0%)	x (100.0%)
	Any Reason for Exclusion	x (xx.xx%)	x (xx.xx%)	x (xx.xx%)
	[Reason 1]	x (xx.xx%)	x (xx.xx%)	x (xx.xx%)
	[Reason 2]	x (xx.xx%)	x (xx.xx%)	x (xx.xx%)
	...			
Per Protocol Population	Number of participants	x (100.0%)	x (100.0%)	x (100.0%)
	Any Reason for Exclusion	x (xx.xx%)	x (xx.xx%)	x (xx.xx%)
	[Reason 1]	x (xx.xx%)	x (xx.xx%)	x (xx.xx%)
	[Reason 2]	x (xx.xx%)	x (xx.xx%)	x (xx.xx%)
	...			

Table 9: Prior Medications – Safety Population

WHO Drug Dictionary ATC Level 1/ Level 3	ROTAVIN N=XX x (%)	ROTAVIN- M1 N=XX x (%)	Total N=XX x (%)
Any prior medication	x (x)	x (x)	x (x)
ATC Level 1 - 1	x (x)	x (x)	x (x)
ATC Level 3 - 1	x (x)	x (x)	x (x)
ATC Level 3 - 2	x (x)	x (x)	x (x)
...	x (x)	x (x)	x (x)
ATC Level 1 - 2	x (x)	x (x)	x (x)
ATC Level 3 - 1	x (x)	x (x)	x (x)
ATC Level 3 - 2	x (x)	x (x)	x (x)
...	x (x)	x (x)	x (x)

N=Total number of participants in the safety population in each vaccine group and overall.
x=Number of participants with a prior medication
Percentages are based on the total number of participants in the safety population in each vaccine group and overall.
A participant may be counted in multiple rows within each ATC Level 1 classification; however, they will be counted only once in the overall row for the ATC Level 1 classification. Therefore, the sum of participants within each ATC Level 1 classification may not add up to the overall row for the ATC Level 1 classification.
All medications coded and reviewed on WHO Drug version XX.

Programming note: Medications may be sorted by descending frequency of ATC Level 1 and/or Level 3 classifications.

Table 10: Concomitant Medications – Safety Population – After Any Dose

{This table will be similar to Table 9}

Table 11: Concomitant Medications – Safety Population – After Dose 1

{This table will be similar to Table 9}

Table 12: Concomitant Medications – Safety Population – After Dose 2

{This table will be similar to Table 9}

Table 13: Concomitant Vaccinations – Safety Population

	ROTAVIN N=XX x (%)	ROTAVIN-M1 N=XX x (%)	Total N=XX x (%)
Any Concomitant Vaccination	x (x)	x (x)	x (x)
BCG vaccine	x (x)	x (x)	x (x)
Hepatitis b vaccine	x (x)	x (x)	x (x)
Polio vaccine live oral	x (x)	x (x)	x (x)
Diphtheria vaccine toxoid; Hepatitis b vaccine; HIB vaccine; Pertussis vaccine; Tetanus vaccine toxoid	x (x)	x (x)	x (x)
Pneumococcal vaccines	x (x)	x (x)	x (x)
Other	x (x)	x (x)	x (x)

N=Total number of participants in the safety population in each vaccine group and overall.

x=Number of participants with a concomitant vaccination

Percentages are based on the total number of participants in the safety population in each vaccine group and overall

For participants with at multiple Concomitant vaccinations, the participant may be counted in multiple rows corresponding to different vaccinations; however, they will be counted only once in the “Any Concomitant Vaccination” row. Therefore, the sum of participants may not add up to the “Any Concomitant Vaccination” row.

Table 14: Geometric Mean Concentration (GMC) for IgA – PP Population

Day		ROTAVIN	ROTAVIN-M1	GMC Ratio (95% CI ^b)	Adjusted GMC Ratio (95% CI) ^c
Day 1	Number of observations	xx	xx		
	Mean (SD) Log10 Concentration	xx.xx (xx.xxx)	xx.xx (xx.xxx)		
	GMC	xx	xx		
	95% CI ^a of GMC	(xx, xx)	(xx, xx)		
	Range (Min, Max) of Concentration	(xx, xx)	(xx, xx)		
Day 85	Number of observations	xx	xx		
	Mean (SD) Log10 Concentration	xx.xx (xx.xxx)	xx.xx (xx.xxx)	xx.xx (xx.xx, xx.xx)	xx.xx (xx.xx, xx.xx)
